5.2.2 North Star Ambulatory Assessment

The NSAA is a functional scale specifically designed for ambulant patients affected by DMD. It is designed to test 17 activities (see [Appendix 2](#)) with scores of 0, 1 or 2 for each activity; a higher score indicating fewer limitations due to DMD. The total score will be derived as the sum of the scores from the 17 activities, and hence has the range 0-34. If the NSAA was performed but some of the activity scores are missing, then the worst score of the adjacent visits will be used to calculate the total score. For example, if the Week 24 NSAA was performed but some of the activities were missing then the worst score for the corresponding activity at Week 12 and 36 will be used.

The NSAA linearized score will also be derived ([Mayhew 2013](#)) where the NSAA scale is converted to a 0-100 scale using 16 of the activities (excludes 'lifts head').

The time to rise from the floor (time to stand) and the 10-Metre run/walk time are also collected with this assessment and are described in sections below as independent endpoints.

If the subject is unable to perform the assessment the reason will be recorded. If the reason given for not performing the assessment is related to the subject's medical condition (i.e. informative) the activity score will be taken as zero, otherwise it will be taken as missing.

Changes from baseline in the total score and the linearized score will be calculated.

The following velocities of change (change per month) will also be calculated for the total and linearized scores:

- Baseline to Week 12
- Week 12 to Week 24
- Week 24 to Week 36
- Week 36 to Week 48

And

- Baseline to Week 24
- Week 24 to Week 48

... and so forth when reporting the extension phase data

Loss of ambulation will be determined by a score of 0 with the 'walk' activity in the NSAA. To ensure the subject's disease has truly reached this level, subsequent visits will also need to have a score of 0.

The number of functions (0, 1, 2...) a subject has lost ("unable"), compared to baseline, will also be determined at each visit. Again, to ensure, that the subject's disease has truly reached this level subsequent visits will also need to have a score of 0.

5.2.3 10-Metre Run/Walk

The 10-metre run/walk should be performed once at each visit and only repeated if the evaluator deems it to be spurious. The protocol incorrectly states that the test should be repeated after a 10 minute rest and both times recorded on the eCRF. The error was documented in a file note (SMTC11005-006 Dated: 05Oct2017). As a consequence, the majority of patients only have one test performed at a visit however if there is a repeat test then the shortest time (duration) of the completed tests will be used in analyses. If the subject is unable to perform the assessment or is unable to complete it, the reason will be recorded. For an assessment not completed the distance and duration of time walked will also be recorded.

If the reason given for not performing at any assessment or not completing any assessment is related to the subject's medical condition (i.e. informative) the time will be taken as the worst score recorded (over all subjects and assessments) whilst on treatment or the derived time adjusted for the distance recorded respectively.

The derived time adjusted for the distance = (10/distance in metres) x time recorded.

Changes from baseline will be calculated.

The following velocities of change (change per month) will also be calculated:

- Baseline to Week 12
- Week 12 to Week 24
- Week 24 to Week 36
- Week 36 to Week 48

And

- Baseline to Week 24
- Week 24 to Week 48

... and so forth when reporting the extension phase data

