5.0 Definitions and Study Assessments

5.1 Definitions

Baseline

Unless stated otherwise, the baseline is defined as the last non-missing assessment prior to the first administration of investigational medicinal product (IMP). If the assessment time is missing while the assessment date is the same date as the first administration of investigation product, a scheduled pre-dose assessment will be considered as baseline.

Change from Baseline

Change from baseline is defined as (value at post-baseline visit – value at baseline). Similarly percentage change from baseline is defined as $100 \times (\text{change from baseline})/\text{baseline}$.

Concomitant and Prior Medication

Prior medications are defined as medications with a start date prior to first dose of IMP. Concomitant medications are defined as any medications ongoing at the start of IMP treatment or with a start date on or after the first IMP dose date. Consequently, medications ongoing at the start of IMP will be reported as both prior and concomitant medications.

Study Day 1

The first day IMP is administered.

Study Day

Study day is defined as the number of days from Study Day 1.

- Before Study Day 1, Study Day = (Date of Interest – Date of Study Day 1)
- On or After Study Day 1, Study Day = (Date of Interest – Date of Study Day 1) + 1

Therefore the day prior to Study Day 1 is Study Day -1.

Study Visit

For by-visit summaries, data will be assigned to visits using windowing (see below). If more than one actual visit (including the early termination or unscheduled visits) falls within the same defined window, the visit closest to the target day with non-missing data will be considered for analysis. If two actual visit dates are at the same distance from the target day, the latest visit with non-missing data will be considered for analysis.

| Study Analysis Visit | Target Day | Study Day | Interval (days) |
|--|--------------------------|----------------------------|-------------------------------|
| Baseline | 1 | ≤1* | NA |
| Day 7 (Cohorts 2 & 3 only) | 7 | 5 to 9 | 5 |
| Week 4 | 28 | 21 to 38 | 18 |
| Week 8 | 56 | 49 to 66 | 18 |
| Week 12 | 84 | 67 to 112 | 46 |
| Week 24 | 168 | 140 to 196 | 57 |
| Week 36 | 252 | 224 to 280 | 57 |
| Week 48 | 336 | 308 to 364 | 57 |
| Week 60 | 420 | 392 to 448 | 57 |
| Week W | W x 7 | (W x 7 -28) to (W x 7 +28) | 57 |
| And so forth for 3 monthly visits | | | |

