5.2 Efficacy Assessments

All of the efficacy endpoints will be assessed at baseline, end of study, and Weeks 12, 24, 36 and 48 during the first 48 weeks and then 6 monthly during the extension phase. If a subject withdraws from the study prematurely they will also be assessed at the termination visit.

The 6MWT will also be conducted at screening.

In the sections below reference is made to reasons for not performing an assessment or not completing an assessment. Different approaches will be taken for dealing with the missing data dependent on whether or not the reason is related to the subject's medical condition (i.e. informative). A reason of 'Subject physically unable' will be regarded as informative, whilst 'Site staff/facility unavailable' is not informative. Other reasons will require a team review on a case-by-case basis.

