7.0 Interim Analyses

While the study is in progress, a Data Monitoring Committee (DMC) will conduct planned reviews of the study data to evaluate the safety, tolerability and activity of the study drug treatment. Detailed information can be found in the DMC Charter and Data Monitoring Analysis Plan.

An interim analysis will also be conducted when all subjects in Cohorts 1 and 2 have completed their Week 24 visit. This interim analysis will only include Cohort 1 and 2 efficacy and pharmacodynamic data till Week 24. All safety data from Cohorts 1 and 2 will be presented, though the key data for the interim analysis will be data reported till Week 24. The tables generated for the interim analysis are identified in the list of TFLs.

The main clinical study report (CSR) will be written when all subjects in Cohorts 1 and 2 have completed their Week 48 visit. This CSR will include all available data from these two cohorts (including extension data) and serious adverse event data from Cohort 3.

Further analyses will be conducted when all subjects in Cohort 3 have completed their Week 48 visit and prior to submission. The final reporting of data from this study will be conducted at the end of the study (when SMT C1100 is either approved in the relevant countries or development of SMT C1100 is discontinued).

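### Read literally, the NSAA missing-item rule fills baseline from an on-treatment visit, and it allows the same Week 24 test to score lower in the main report than at the interim

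*SAP*

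**What the plan says.** SAP 5.2.2 describes 17 activities "with scores of 0, 1 or 2 for each activity; a higher score indicating fewer limitations due to DMD", giving a total of 0 to 34. If the test was done but items are missing, "then the worst score of the adjacent visits will be used to calculate the total score". The only example is Week 24, where "then the worst score for the corresponding activity at Week 12 and 36 will be used". The section does not exempt baseline, does not limit the rule to post-dose visits, and does not say what to do when only one neighbour exists. SAP 9.1.1 adds that a wholly missed visit is not imputed.

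On timing, SAP 5.2 states that "All of the efficacy endpoints will be assessed at baseline, end of study, and Weeks 12, 24, 36 and 48 during the first 48 weeks". The only extra pre-dose test it names is the walk test: "The 6MWT will also be conducted at screening". The protocol's Time and Events Table agrees for Cohorts 1 and 2 (NSAA at baseline, then Weeks 12, 24, 36 and 48). For Cohort 3 that table has the NSAA at screening, Week 24 and Week 48 within the treatment phase.

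SAP 5.1 gives the general rule, subject to exceptions stated elsewhere, that "the baseline is defined as the last non-missing assessment prior to the first administration of investigational medicinal product (IMP").

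SAP 7.0 states: "An interim analysis will also be conducted when all subjects in Cohorts 1 and 2 have completed their Week 24 visit". It limits the interim's efficacy data to Week 24. The main report follows once Cohorts 1 and 2 have completed Week 48.

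**The concern.** Two separate problems follow from an adjacent-visit rule that looks both ways.

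First, a partly completed baseline test has no earlier scheduled NSAA to borrow from, so the neighbour is an on-treatment visit. Every NSAA change, velocity from baseline and plot against baseline for that boy would then rest on a starting value that is partly post-dose. In a study with no control arm, within-boy change is the main way to look at activity.

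Second, the Week 24 fill needs Week 36, which the interim excludes. The same Week 24 test can therefore have one total at the interim and a lower one in the main report. Because the later score is borrowed backwards, decline after Week 24 can also be shown as decline before it. That matters for SAP 9.6.1, which compares the Week 24 to 48 velocity with the baseline to Week 24 velocity.

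**Working it through.** The plan gives no figure on this point, so there is none to reproduce. Inputs: item scale 0, 1 or 2, with higher better, so the worst score is the minimum (SAP 5.2.2); visit schedule (SAP 5.2 and the protocol's Time and Events Table); interim cut at Week 24 (SAP 7.0); about 30 + 10 = 40 boys in Cohorts 1 and 2 (SAP 3.1), tabulated together (SAP 9.6.1).

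**1. Missing baseline item, Cohorts 1 and 2.** Let B be the true baseline score, W12 the Week 12 score and V the score at a later visit.
- With one neighbour there is no worst of two to take; the fill is W12.
- Change to Week 12 = W12 - W12 = 0, whatever B was.
- Error in any later change = (V - W12) - (V - B) = B - W12. With both scores between 0 and 2, this runs from -2 to +2.
- If the boy worsened by Week 12 (B above W12), the error is positive and decline is understated. If he improved, the error is negative and improvement is understated.

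The same algebra holds in Cohort 3 with Week 24 in place of Week 12.

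**2. Missing Week 24 item.** The interim fill is W12. The main-report fill is min(W12, W36). Of the 9 possible pairs of scores, 3 differ:

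| Week 12 | Week 36 | Interim fill | Main-report fill | Shift |
|---|---|---|---|---|
| 1 | 0 | 1 | 0 | -1 |
| 2 | 1 | 2 | 1 | -1 |
| 2 | 0 | 2 | 0 | -2 |

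The other 6 pairs give no shift, and no pair gives an upward one. Baseline and Week 12 fills cannot change after the interim, because all their neighbours lie within Week 24.

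**3. Velocities.** Take one item truly scored 2, 2, 2, 1, 1 at baseline and Weeks 12, 24, 36 and 48, with the Week 24 score missing. SAP 9.6.1 divides each 24-week change by 6.
- True: baseline to Week 24 = (2 - 2)/6 = 0; Week 24 to 48 = (1 - 2)/6 = -1/6; difference = -1/6 point per month.
- Filled with min(2, 1) = 1: baseline to Week 24 = (1 - 2)/6 = -1/6; Week 24 to 48 = (1 - 1)/6 = 0; difference = +1/6.

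For this item, worsening after Week 24 becomes an apparent slowing of decline.

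**4. Size.** One boy with a 2-point error moves a mean of 40 by 2/40 = 0.05 points. If 1 to 4 boys shift by 1 to 2 points, the mean moves by between 1/40 = 0.025 and 8/40 = 0.20 points.

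The documents do not say how many tests are partly completed or how often items decline. As an illustration only, let q be the chance that an item falls one level between Weeks 12 and 36, with items independent. The chance that a boy's Week 24 total changes between reports is 1 - (1 - q)^m for m missing items:

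| Missing items | q = 0.02 | q = 0.20 |
|---|---|---|
| 1 | 2% | 20% |
| 3 | 6% | 49% |
| 5 | 10% | 67% |

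**The case against.** The strongest reply is that SAP 5.2.2 never tells anyone to fill baseline from Week 12. Its example is a post-dose visit with neighbours on both sides, and SAP 5.1 keeps baseline pre-dose unless an exception is stated. A programmer could reasonably follow 5.1. This stands in part: the conflict comes from a literal reading, not from an explicit instruction. But the rule covers any performed NSAA without exception, so the choice is left to whoever writes the derivation.

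A reader might also infer that a worst-score fill at baseline always lowers the starting value and so manufactures improvement. The documents do not support that. With one neighbour the fill is simply that visit's score and can err either way. It cannot show improvement at the filling visit, and it shows false improvement later only if the item recovers above the filled score.

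Nor does the Week 24 total necessarily change between reports. That needs both a partly completed Week 24 test and a Week 36 item below its Week 12 score.

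Several mitigations are fair:
- Inability is normally scored 0 (SAP Appendix 2), and tests not performed for medical reasons are set to zero, so the rule reaches mainly residual gaps.
- Counts of imputed values are planned (SAP 9.1 and 9.6.1). SAP 9.1 introduces them for imputation on medical grounds, so it is not certain that item fills are included.
- The interim has no stated NSAA decision rule, and its database is frozen, not locked (SAP 8.2).

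Finally, using only earlier scores would be last observation carried forward, which can hide decline in a progressive disease. That is a good reason not to prescribe it as the replacement.

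**Conclusion.** The point holds as a minor correction. On the literal rule, a missing baseline item takes an on-treatment score, in conflict with SAP 5.1. That item's change to the filling visit is forced to zero, and later changes carry an error of up to 2 points per item whose direction is not known in advance. Week 24 totals with filled items can fall by 1 to 2 points per item between the interim and the main report, and the backward fill can move decline from after Week 24 to before it in the velocity comparison.

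The effect on group means is small, and the NSAA is an exploratory endpoint in an unpowered study. The 0.05-point figure assumes a boy whose item differs by the full 2 points and a mean over 40; the range up to 0.20 assumes at most 4 boys affected by 2 points each. The number of partly completed tests is not given, so how often any of this occurs is unknown.

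**What to change.** In SAP 5.2.2:
- State that baseline items are never filled from post-dose assessments. Use a pre-dose value if there is one; otherwise set the baseline total to missing or pro-rate it from the completed items. Pro-rating treats the missing item as being as hard as the others, so it should come with a limit on the number of missing items.
- For post-baseline visits, state what is done when only one neighbour is available.
- Mark interim Week 24 totals that contain filled items as provisional.
- Add a sensitivity summary of NSAA changes and velocities that leaves out filled totals.

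The two-neighbour rule for later visits need not be replaced; the sensitivity summary will show whether it matters. The cost is a few lines of SAP text, a small change to the derivation and one extra set of summaries. No new data are needed.

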6.5.1. North Star Ambulatory Assessment

The NSAA should be performed without shoes at the times outlined in the Time and Events Table.

Where possible this should be carried out by the same assessor in order to reduce variability. A copy of the instructions for patients and an example score sheet can be found in the Study Reference Manual. The order of the assessments is important and needs to be followed precisely.

6.5.2. 10-Metre Run or Walk

The 10-metre run or walk should be performed at the times outlined in the Time and Events Table and as referenced in the Study Manual.

A 10-metre straight course should be plotted out. Patients should be asked to complete the course as quickly as they can. Patients should start from immediately behind the start line and the time should start from the moment they cross the line until they reach 10 meters. Patients should be asked to repeat the test after a 10 minute rest and both times will be recorded in the source documents and transcribed to the CRF.

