12.1.5. Missing, Unused and Spurious Data

Missing data will be accounted for in all summaries by time, with reasons provided where possible (e.g., discontinuation). If any data are excluded from analyses the reason for their exclusion will be documented in the clinical study report.

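### SAP 5.2.3 analyses the shortest completed 10-metre time even when the first run was rejected as spurious, so a falsely fast run is kept, and best-of-two values may be mixed with single-run values

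*SAP*

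**What the plan says.** SAP 5.2.3 sets the procedure: "The 10-metre run/walk should be performed once at each visit and only repeated if the evaluator deems it to be spurious". In the same paragraph it sets the value to be analysed: "if there is a repeat test then the shortest time (duration) of the completed tests will be used in analyses".

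The protocol differs. Section 6.5.2 states: "Patients should be asked to repeat the test after a 10 minute rest and both times will be recorded in the source documents". The SAP comments: "The protocol incorrectly states that the test should be repeated after a 10 minute rest and both times recorded on the eCRF". It refers to a file note dated 05Oct2017 and reports that "the majority of patients only have one test performed at a visit".

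The resulting time feeds the by-visit summaries and changes from baseline (SAP 9.6.4), the velocity estimates (SAP 9.6.1), and the plots against exposure, MRS, biopsy and other functional measures (SAP 9.10.1 to 9.10.4). The endpoint is listed as exploratory in both documents (Protocol 3.3, SAP 4.3). No sensitivity analysis on the choice of run is described.

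**The concern.** There are two separate problems.

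First, the selection rule ignores the reason for the repeat. Under the SAP, a second run exists because the evaluator distrusted the first. If the first was distrusted because it was too fast (a late start or early stop of the watch, or a short course), it will usually be shorter than the valid repeat, and the rule selects it. The word completed removes unfinished runs only, not completed runs that were rejected.

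Second, runs may also have been repeated because the protocol asked for it. In such pairs neither run is spurious, but the shorter of two valid runs is on average shorter than a single run. If a boy has two runs at one visit and one at another, his change from baseline includes a difference that owes nothing to drug or disease. Two runs at baseline and one later looks like decline; the reverse looks like improvement. The study has no concurrent control arm in which such an error would cancel.

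**Working it through.** The documents give no figure to reproduce. The sample size is not powered, and neither the within-visit SD of the 10-metre time nor the share of visits with two runs is stated.

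**Inputs**

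- Repeat rule, selection rule and the statement that most patients have one test: SAP 5.2.3.
- Routine repeat: Protocol 6.5.2.
- Velocity over one 12-week interval, defined as the difference between visits divided by 3: SAP 9.6.1.
- Assumed: within-visit SD s of 0.3 to 0.6 s; difference in repeat share between baseline and the later visit of 0.1 to 0.4; runs independent and normal.

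**1. Spurious first run**

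Let the first run be off by e SDs (negative means too fast) and the repeat be valid. The two were simulated with 1,000,000 pairs per row. The bias of the shortest-time rule is in within-visit SDs.

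| First run off by | Spurious run kept | Bias, shortest time | Bias, repeat used |
|---|---|---|---|
| 3 SD too fast | 98% | -3.01 | 0 |
| 2 SD too fast | 92% | -2.05 | 0 |
| 1 SD too fast | 76% | -1.20 | 0 |
| 1 SD too slow | 24% | -0.20 | 0 |
| 2 SD too slow | 8% | -0.05 | 0 |
| 3 SD too slow | 2% | -0.01 | 0 |

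The fault runs one way: fast errors are kept and slow errors are mostly removed. In seconds, a first run 2 SD too fast leaves that boy's value too short by 2.05 x 0.3 = 0.62 s to 2.05 x 0.6 = 1.23 s. One such boy among the roughly 40 in Cohorts 1 and 2 moves the mean by 0.62/40 = 0.015 s to 1.23/40 = 0.031 s.

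**2. Two valid runs against one**

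For two independent normal runs with the same mean, the expected minimum is mean - s/sqrt(pi) = mean - 0.564 s. Simulation gave -0.563 SD.

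- s = 0.3 s: 0.564 x 0.3 = 0.17 s shorter than a single run.
- s = 0.6 s: 0.564 x 0.6 = 0.34 s shorter.

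For one boy with two runs at baseline and one at Week 12, the velocity shifts by 0.17/3 = 0.06 to 0.34/3 = 0.11 s per month towards worsening.

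For the mean change, shifts cancel in boys with two runs at both visits, so only the difference in share matters:

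bias = 0.564 x s x (share with two runs at baseline - share with two runs at the later visit)

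- Low end: 0.564 x 0.3 x 0.1 = 0.017, about 0.02 s.
- High end: 0.564 x 0.6 x 0.4 = 0.135, about 0.14 s.

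The sign is that of the difference in share, which the documents do not give.

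**The case against.** The strongest reply is that best effort is a legitimate convention. Protocol 6.5.2 asks boys to cover the course as fast as they can, and Protocol 6.4.5 takes the highest FEV1 and FVC. If most recorded pairs come from the routine repeat, neither run is spurious and the first problem does not arise for them. Fatigue on the second run would also make the first run the usual minimum and shrink the shift. This stands in part: for two valid runs, first against best is partly a matter of preference. Best effort does not justify keeping a run the evaluator rejected, and it is a consistent convention only if every visit has the same number of attempts.

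A second reply is that gross timing errors could be caught by data cleaning (Protocol 13.6), by the review before database lock (SAP 8.2), or by exclusion. On exclusion, Protocol 12.1.5 says: "If any data are excluded from analyses the reason for their exclusion will be documented in the clinical study report". These are general provisions. None tells the programmer to set aside a completed run judged spurious, and SAP 5.2.3 gives an explicit rule the other way. By contrast, SAP 5.3.3.1 does allow a biopsy assay value with a technical fault to be excluded if this is justified and documented.

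A reader might also infer that sites made two runs at every visit until the October 2017 file note and one afterwards, so that baselines are systematically best-of-two and the data show false decline. The documents do not say this. They give the date of the note and say that most patients have one test; they do not say which sites repeated, at which visits, or when practice changed.

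**Conclusion.** As written, the rule in SAP 5.2.3 is wrong for a completed run rejected as falsely fast: that run is analysed whenever it is shorter than its repeat. This follows from the text and needs no assumption. Whether any such run was recorded is unknown.

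The mixing of best-of-two and single-run values is a possibility created by the conflict between the protocol and the SAP, not a documented fact. If it occurred, the bias in a mean change is about 0.02 to 0.14 s under the assumed SDs and share differences, with independent and equally valid runs. The direction cannot be stated. A larger figure built on half or more of the boys having two runs at baseline would not fit the SAP's statement that most have one.

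The endpoint is exploratory and no primary or secondary endpoint depends on it, so the effect on the trial's main conclusions is small. The correction is still worth making because it is cheap and the present rule defeats the purpose of the repeat.

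**What to change.** In SAP 5.2.3, replace the shortest-time sentence with two rules.

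1. A run the evaluator judged spurious is excluded and the valid repeat is analysed, whichever is longer.
2. Where two completed runs are recorded and neither is documented as spurious, the visit is flagged, the number of such visits is reported by time point, and both times are listed. The change-from-baseline and velocity analyses are then repeated using the first completed run, as a sensitivity analysis. The shorter time may stay in the main analysis.

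The cost is one SAP paragraph, one extra set of outputs, and a check of source or eCRF comments for the minority of visits with two runs. The documents do not show that the reason for a repeat is captured. Where it is missing, the visit falls under rule 2, which does not need the reason.
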